18.4. LABORATORY EVALUATIONS

Results from the central laboratory will be included in the reporting of this study for hematology, chemistry and urinalysis. Presentation of results for drug-specific laboratory parameters including gantenerumab levels and anti-gantenerumab antibodies are described in [Section 18.7.2](#). A list of expected laboratory assessment visits can be found in the protocol Appendix 3, Section 3.2. [Table C](#) identifies the laboratory parameters and order of parameters to be included in table summaries.

Author:	[REDACTED]	Version Number:	7
	[REDACTED]	Version Date:	07Dec2023
Template No.:	CS_TP_BS016 Revision 6	Reference:	CS_WI_BS005
Effective Date:	02Dec2019		

Copyright © 2009, 2010, 2012, 2016, 2018, 2019 [REDACTED] All rights reserved. The contents of this document are confidential and proprietary to [REDACTED] Holdings Inc. and its subsidiaries. Unauthorized use, disclosure or reproduction is strictly prohibited.

Table C: Laboratory Parameters

Chemistry	Hematology	Urinalysis
ALT (SGPT)	Basophils	Bilirubin
AST (SGOT)	Basophils %	Blood
Albumin-QT	Eosinophils	Clarity
Alkaline Phosphatase-QT	Eosinophils %	Color
Calcium (EDTA)	Hematocrit	Glucose
Cholesterol (High Performance)	Hemoglobin	Ketones
Creat Cir, Cockcroft & Gault	Lymphocytes	Leukocyte Esterase
Creatinine Kinase	Lymphocytes (%)	Nitrate
Creatinine (Rate Blanked)	MCH	Protein
Direct Bilirubin	MCHC	Specific Gravity
GGT	MCV	Urobilinogen
LDH	Monocytes	pH
Magnesium	Monocytes (%)	
Phosphorus	Neutrophils	
Serum Chloride	Neutrophils (%)	

Author: [REDACTED]

Version Number:

7

Version Date:

07Dec2023

Template No.: CS_TP_BS016 Revision 6

Reference: CS_WI_BS005

Effective Date: 02Dec2019

Chemistry	Hematology	Urinalysis
Serum Glucose	Platelets	
Serum Potassium	RBC	
Serum Sodium	WBC	
Serum Uric Acid		
Total Bilirubin		
Total Protein		
Triglycerides		
Urea Nitrogen		

Presentations will use SI Units. Clinical laboratory parameters will be summarized descriptively at each measurement time. Mean and mean change from baseline values will be presented at each study visit for continuous parameters. Change from baseline will be calculated as post-baseline assessment - baseline assessment. If either the baseline or post-baseline value is missing, the observation will not be included in the change from baseline summary. If a laboratory parameter has a value “ $< x$ ”, where x is a numerical number, then the value “ $x/2$ ” will be assigned to the parameter. If a laboratory parameter has a value “ $> x$ ”, then the value “ $1.1x$ ” will be assigned to the parameter.

Author: [REDACTED]

Version Number:

7

Version Date:

07Dec2023

Template No.: CS_TP_BS016 Revision 6

Reference: CS_WI_BS005

Effective Date: 02Dec2019

The following summaries will be provided for laboratory data:

- Observed values and change from baseline by visit for Chemistry, Hematology and Urinalysis (quantitative measurements)
- Observed values for categorical Urinalysis measurements
- Shifts from OLE baseline to annual post-baseline visit for Chemistry, Hematology and Urinalysis
- Shifts from OLE baseline to markedly abnormal value for Chemistry and Hematology
- Listing of subjects with markedly abnormal results for Chemistry, Hematology and Urinalysis
- Listing of all observed values for Chemistry, Hematology and Urinalysis

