1.13.3 Neutropenia in the gantenerumab OLE period

A potential risk of neutropenia with gantenerumab has been observed in a nonclinical mouse study, as has been described in the IB, but has not been observed in nonclinical cynomolgus monkey study or clinical trials, including at the current human target dose levels (based on a total exposure to gantenerumab G3 and G4 product at any dose of approximately 2500 participants [healthy volunteers or AD patients]). Therefore, the frequency of chemistry and hematology laboratories will be increased from annually after year one (OLE V13) to every 6 months thereafter.

The DSMB meeting frequency will be increased from the originally planned every 6 months to quarterly.

The DIAN-TU Medical Monitors will perform quarterly aggregate review of all safety data (MRI findings, AEs, clinical labs, etc.), in addition to review of all MRIs with any change, as is current practice as outlined below in Section 1.14.

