- Vital signs (blood pressure, heart rate, respiratory rate, and body temperature; weight may be obtained approximately every 3 months per Section 6.1.6 of the main protocol)
- Blood collection for the following:
 - CCI
[REDACTED]
 - Stored plasma
- C-SSRS administration
- Urine pregnancy testing for POBCP
- Drug product dosing and post-dose monitoring/evaluation as specified in Section 2.5
- Phone call (not required at all home/off-site visits but direct site-participant contact should occur at least once every 3 months throughout the study): the DIAN-TU site coordinator calls participant and addresses any concerns, discusses scheduling of safety MRI and next visits, and encourages compliance.

3.2.5 OLE VISITS 13, 27, and 40 or Early Termination: ANNUAL VISIT AT DIAN-TU SITE

Location: DIAN-TU site

Timing: 48 and 104, and 156 weeks \pm 7 days (or Early Termination) from day of first dose at OLE Visit 1; approximately a 2- to 3-day visit. The second dose administration for Q2W dosing associated with each visit should be completed at weeks 50, 106, and 158 weeks \pm 3 days, respectively, and will include vitals, concomitant medications, and AEs as outlined in the Schedule of Visits. The sequence and timing of visit procedures is very important.

Requirements and suggested timing of study procedures are detailed in the *Global Manual of Operations*. For participants who live near the study site, these visit procedures may be scheduled over a longer time period of up to 2 weeks.

Procedures:

- Concomitant Medications
- Adverse Event Assessment
- Vital signs (blood pressure, heart rate, respiratory rate, and body temperature); weight and height
- Administration of C-SSRS

- Blood collection for the following:
 - Clinical laboratory tests (hematology, chemistry, urinalysis)
 - CCI [REDACTED]
- Urine pregnancy testing for POCBP
- Physical and neurological examination
- Clinical assessments:
 - Clinical Dementia Rating (CDR) including calculation of Clinical Dementia Rating Sum of Boxes (CDR-SB)
 - Assessment of clinical diagnosis and clinician judgment of symptoms
 - CCI [REDACTED]

OTE: For each participant, the CDR and assessment of clinical diagnosis should be administered by the same experienced clinician at all visits. Whenever possible the CDR rater should not be involved in other clinical assessments (e.g., MMSE, FAS, GDS, NPI-Q) or in cognitive testing.

- Complete Cognitive Battery (see Section 3.2)
- CCI [REDACTED]

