- Lumbar Puncture (LP) should be conducted as close to the participant's double-blind CCI [REDACTED]
- Annual MRI (including structural and functional MRI) uploaded immediately to ensure reading obtained prior to dosing. This MRI includes safety MRI sequences. MRI should be performed before lumbar puncture, if on the same date.
- Drug product dosing and post-dose monitoring/evaluation as specified in Section 2.5 for OLE V13 and OLE V27; no drug administration should occur at OLE V40 or an early termination visit.
- Follow-up phone call or brief visit within 24 hours after LP, and no longer than 48 hours later, to review any adverse events.

3.2.6 OLE Visits 20 and 33

Location: DIAN-TU site or participant's home or other trial-identified location with the trial-designated home health nurse.

Timing: 76 and 128 weeks \pm 3 days from day of first dose at OLE Visit 1. The second dose administration for Q2W dosing associated with each visit should be completed at weeks 78 and

130 ± 3 days, respectively, and will include vitals, concomitant medications, and AEs as outlined in the Schedule of Visits.

Procedures:

- Cognitive Battery Subset (Section 3.2)
- Mini-Mental State Examination (MMSE)
- Concomitant medication review
- Adverse event assessment
- Vital signs (blood pressure, heart rate, respiratory rate, and body temperature; weight may be obtained approximately every 3 months per Section 6.1.6 of the main protocol)
- C-SSRS administration
- Blood collection for the following:
 - Clinical laboratory tests (hematology, chemistry)
 - Stored Plasma
- Urine pregnancy testing for POCBP
- Drug product dosing and post-dose monitoring/evaluation as specified in Section 2.5
- Phone call (not required at all home/off-site visits but direct site-participant contact should occur at least once every 3 months throughout the study): the DIAN-TU site coordinator calls participant and addresses any concerns, discusses scheduling of safety MRI and next visits, and encourages compliance

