16. All participants enrolled in OLE for gantenerumab will start at the **CCI** [REDACTED] dose **CCI** [REDACTED] and will up-titrate to **CCI** [REDACTED]; then at increased dosing frequency of **CCI** [REDACTED] to a target dose of **CCI** [REDACTED]. Participants should receive at least three doses at each Q4W titration step up to **CCI** [REDACTED] 4 weeks (\pm 4 days) apart, before proceeding to the next titration step. Participants should receive six doses of **CCI** [REDACTED] 2 weeks (\pm 3 days) apart before proceeding to the final titration step of

CCI 2 weeks (\pm 3 days) apart. The titration schema was designed to reach the target dose of **CCI** administered every 2 weeks; however, the target dose may not be achieved as otherwise dictated ARIA-E and ARIA-H management algorithms (Section 1.14) or more conservative action by the site principal investigator/DIAN-TU Medical Monitors. If needed, the schedule of assessments will be adjusted. Dosing visits occurring every 2 weeks will be identified/labeled as one visit. The first portion of the visit will include completion of any required visit procedures and dosing; two weeks \pm 3 days after, the second dose will be administered.

- 17. Site study coordinators should call participants either during or within two weeks after OLE V2 and OLE V3. For OLE V4 and subsequent home visits, coordinator calls can be made with less frequency at the discretion of the PI or designee, and/or coordinator, and participant, but should occur at least every 3 months.
- 18. For OLE V20 and OLE V33, chemistry and hematology are required; no urinalysis is needed.
- 19. A sentinel cohort of the first 20 participants to titrate beyond **CCI** every **C** weeks will have an additional safety MRI performed after the first two doses of **CCI** administered two weeks apart (Week 51, SC1-MRI) prior to up-titrating to **CCI**; and after the first **CC** doses of **CCI** administered two weeks apart (Week 63, SC2-MRI). The DIAN-TU Medical Monitors will review the individual and aggregate data to ensure there are no safety findings warranting more frequent MRI for all participants.
- 20. Any participant not having initiated up-titration at any point should use the MRI label of OSM4 for this safety MRI.
- 21. For plasma collection only at this visit.
- 22. Clinical laboratory tests (hematology, chemistry, urinalysis) at the discretion of the investigator.

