18.4.1. LABORATORY REFERENCE RANGES AND MARKEDLY ABNORMAL CRITERIA

For each visit, laboratory results will be classified as low (L), normal (N), and high (H) according to the laboratory-supplied normal range. The shift from baseline will be presented for each annual post-baseline visit.

A laboratory value is considered Critically High or Critically Low if it exceeds a pre-defined threshold as set by the laboratory vendor. All values for a parameter will be listed for a subject when at least one value for that parameter is identified as Critically High or Critically Low by the laboratory vendor.

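### The SAP's low/normal/high laboratory shift is annual only, so below-range neutrophil and white-cell counts are not tabulated at weeks 76 and 128, the two draws added for the potential neutropenia risk

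*SAP*

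**What the plan says.** **Protocol, Appendix 3 (gantenerumab), Section 1.13.3.** The section opens with the risk: "A potential risk of neutropenia with gantenerumab has been observed in a nonclinical mouse study". It adds that this has not been seen in the monkey study or in clinical trials, with roughly 2,500 people exposed. It then draws the consequence: "Therefore, the frequency of chemistry and hematology laboratories will be increased from annually after year one (OLE V13) to every 6 months thereafter".

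**Protocol, Appendix 3, visit sections and schedule.** The added visits are OLE V20 and V33, timed in Section 3.2.6 at "76 and 128 weeks". Footnote 18 to the OLE schedule of visits fixes what is drawn: "For OLE V20 and OLE V33, chemistry and hematology are required; no urinalysis is needed". The annual visits V13, V27 and V40 are timed in Section 3.2.5: "Timing: 48 and 104, and 156 weeks".

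**SAP, Sections 18.4 and 18.4.1.** The list of laboratory outputs includes "Shifts from OLE baseline to annual post-baseline visit for Chemistry, Hematology and Urinalysis". Section 18.4.1 says that results are classified as low, normal or high at each visit, but restricts the presentation: "The shift from baseline will be presented for each annual post-baseline visit". The other laboratory outputs (by-visit observed values and change, shift to markedly abnormal values, and listings) carry no annual restriction.

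**The concern.** The protocol gives a specific reason for the extra hematology, and the SAP's normal-range table does not use it. A reader who wants to know how many participants went from normal to low neutrophils will turn to the shift table. That table says nothing about weeks 76 and 128. Someone with a count below the normal range at week 76 who is back in range at week 104 would show no shift.

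Timing adds to this. On the nominal schedule the two highest dose steps start at week 48 and week 60, so week 76 is the first scheduled look at hematology under either of them. At stake is a simple descriptive count for a named safety risk at doses above those tested before.

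**Working it through.** The SAP states no figure to reproduce here. The check compares the visit schedule with the outputs.

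**1. Count the scheduled post-baseline hematology visits.** From Protocol Appendix 3, Sections 3.2.5 and 3.2.6 and the schedule of visits:

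| OLE visit | Week | Annual? | In the low/normal/high shift? |
|---|---|---|---|
| V13 | 48 | yes | yes |
| V20 | 76 | no | no |
| V27 | 104 | yes | yes |
| V33 | 128 | no | no |
| V40 | 156 | yes | yes |

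Covered: 3 of 5. Not covered: 2/5 = 40%, which is exactly the two added draws. The count leaves out the early termination visit (its timing is not fixed) and the safety follow-up (laboratory tests there are at the investigator's discretion).

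**2. Place the draws against the dose steps.** Appendix 3, Section 1.5.2.3, names the two sentinel dose levels as 1020 mg and 1500 mg every two weeks. Schedule footnote 19 puts the sentinel MRIs at weeks 51 and 63, each after the first two doses of a step. The steps therefore start at weeks 48 and 60. Footnote 14 gives about 22 target-dose administrations by week 104; dosing every two weeks from week 60 to week 102 gives (102 − 60)/2 + 1 = 22, which agrees. The week 48 draw thus belongs essentially to the lower steps. Draws after week 60 are at weeks 76, 104, 128 and 156, of which 2 of 4 are outside the shift table, including the first.

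**3. Could visit windows bring the two draws in?** SAP Section 6.4 gives yearly data a window of 182 days either side and uses the value closest to the planned date.

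- Week 76 to week 48: 28 × 7 = 196 days, outside.
- Week 76 to week 104: 28 × 7 = 196 days, outside.
- Week 76 to a nominal week 52 (SAP Appendix 1 labels year 1 as week 48/52): 24 × 7 = 168 days, inside.
- Week 128 to week 104: 24 × 7 = 168 days, inside.
- Week 128 to week 156: 28 × 7 = 196 days, outside.

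Even where a draw falls inside, it is used only if it is the closest value, which in effect means that the annual draw is missing. If laboratory data are handled as semi-annual (91 days either side), neither draw can enter an annual slot. Windowing does not reliably close the gap.

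**4. What else shows a week 76 or week 128 result?**

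| Output | Includes weeks 76 and 128? | Counts participants below normal range? |
|---|---|---|
| By-visit observed values and change (SAP 18.4; minimum reported under Section 6 and Appendix 1) | yes | no |
| Shift to markedly abnormal (SAP 18.4) | yes | only past the vendor's critical limit |
| Adverse event tables, overall and by dose level (SAP 18.1) | if recorded as an event under Protocol 6.1.10 and 7.1.1 | only clinically meaningful cases |
| Listing of all values | yes | no |
| Low/normal/high shift | no | yes, at annual visits |

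The shift table is the only laboratory output that counts participants against the normal range, and it is the one that omits these visits.

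**The case against.** The strongest reply is that little is hidden. The by-visit summaries print the minimum, so the lowest neutrophil and white-cell values at weeks 76 and 128 will be visible. A vendor-critical value reaches the markedly abnormal shift, and then all of that participant's values for the parameter are listed. Clinically meaningful abnormalities become adverse events and are tabulated without regard to annual visits. Section 1.13.3 also answers the risk operationally, with quarterly DSMB meetings and quarterly aggregate review by the Medical Monitors; it does not name the shift table as its instrument. The risk comes from a mouse study, the OLE is single-arm with no planned safety comparison, and the study report is abbreviated after early termination.

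All of this stands, and it limits the point. A reader might infer that the week 76 and 128 results are dropped from the analysis, or that the report as a whole could show no neutropenia signal when one exists. The documents do not support either reading, because the other outputs include these draws.

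A reader might also infer that early termination makes the uncovered share of target-dose draws larger. That is not shown. Counting scheduled draws after week 60, the uncovered share is 1 of 1 if the last draw is week 76, 1 of 2 at week 104, 2 of 3 at week 128 and 2 of 4 at week 156. It depends on when each participant stopped and on whether an early termination draw was taken, and the documents give neither.

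The reply does not supply the missing count. A minimum shows one participant's value, and a listing leaves the reader to do the counting.

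**Conclusion.** The point holds as a gap in presentation. The number of participants shifting to below-range neutrophils or white cells is not tabulated at 2 of 5 scheduled post-baseline hematology visits, and those two were added because of the potential neutropenia risk. No estimate, test or decision rule changes, and no data are lost.

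This rests on four assumptions:

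- Annual means V13, V27 and V40, as Protocol Appendix 3, Section 3.2.5, uses the term.
- Markedly abnormal, for laboratory values, means the vendor's critical limits, the only such criterion in SAP 18.4.1. How far those limits lie from the normal range is not stated, so the number of results falling between them cannot be sized.
- The dose timing is nominal. Appendix 3, Sections 2.2 and 3.2.9.1, allow for participants whose weeks do not align after Amendment 11, and ARIA rules can delay titration, so week 76 is not the first draw on the higher steps for everyone.
- The SAP cites protocol amendment 12, while the protocol reviewed is dated 05 Apr 2023. SAP 18.4 sends the reader to Appendix 3, Section 3.2, for laboratory visits, and in the protocol reviewed that section includes weeks 76 and 128.

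**What to change.** In SAP Sections 18.4 and 18.4.1:

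- Present the low/normal/high shift from OLE baseline for hematology and chemistry at every scheduled post-baseline visit: V13, V20, V27, V33 and V40.
- Add a shift from OLE baseline to the worst post-baseline value, taken over all scheduled, unscheduled and early termination draws.
- Keep the urinalysis shift annual, because urinalysis is not collected at V20 or V33.

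The cost is a change of SAP wording, two more visit blocks and one worst-value block in an existing table. The results are already collected, and 18.4.1 already classifies them at each visit. The downside is that a worst-value summary over several draws will show somewhat more out-of-range results by chance than any single visit, so a footnote should say so.

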18.4.1. LABORATORY REFERENCE RANGES AND MARKEDLY ABNORMAL CRITERIA

For each visit, laboratory results will be classified as low (L), normal (N), and high (H) according to the laboratory-supplied normal range. The shift from baseline will be presented for each annual post-baseline visit.

A laboratory value is considered Critically High or Critically Low if it exceeds a pre-defined threshold as set by the laboratory vendor. All values for a parameter will be listed for a subject when at least one value for that parameter is identified as Critically High or Critically Low by the laboratory vendor.

18.5. ECG EVALUATIONS

ECG evaluations are not scheduled after the OLE Baseline measurement. Therefore, no table summaries of ECG findings will be produced for the OLE. Any data collected during the OLE

Author: [REDACTED]

Version Number:

7

Version Date:

07Dec2023

Template No.: CS_TP_BS016 Revision 6

Reference: CS_WI_BS005

Effective Date: 02Dec2019

will be included in a listing of ECG findings sorted by subject, visit and parameter. Potential parameters to be included in the listing if collected include:

- PR Interval (msec)
- QRS Interval (msec)
- QTcF Interval (msec) [derived]
- QTcB Interval (msec) [derived]
- HR (bpm)
- Overall assessment of ECG (Investigator's judgment):
 - Normal
 - Abnormal, Not Clinically Significant (ANCS)
 - Abnormal, Clinically Significant (ACS)

18.6. VITAL SIGNS

The following Vital Signs measurements will be reported for this study:

- Systolic Blood Pressure (mmHg)
- Diastolic Blood Pressure (mmHg)
- Heart Rate (bpm)
- Respiratory Rate (breaths/min)
- Temperature (°C)
- Weight (kg)
- Height (cm)

[REDACTED] [REDACTED]

Author: [REDACTED]

Version Number:

7

Version Date:

07Dec2023

Template No.: CS_TP_BS016 Revision 6

Reference: CS_WI_BS005

Effective Date: 02Dec2019

The following summaries will be provided for vital signs data:

- Observed values and change from baseline by visit (blood pressure, heart rate, respiratory rate and temperature)
- Incidence of post-baseline markedly abnormal values (blood pressure, heart rate, respiratory rate and temperature)
- Observed values and change from baseline by visit for Weight
- Observed values for Height
- A listing of all vital sign data will be presented for the OLE.

18.6.1. VITAL SIGNS MARKEDLY ABNORMAL CRITERIA

Markedly abnormal quantitative Vital Signs measurements will be identified in accordance with the following predefined markedly abnormal criteria in [Table D](#).

Table D: Post-Baseline Markedly Abnormal Vital Sign Criteria

Variable	Unit	Low	High
Systolic Blood Pressure	mmHg	≤ 90 mmHg AND decrease from baseline ≤ 20 mmHg	≥ 180 mmHg AND increase from baseline ≥ 20 mmHg
Diastolic Blood Pressure	mmHg	≤ 50 mmHg AND decrease from ≤ 15 mmHg	≥ 105 mmHg AND increase from baseline ≥ 15 mmHg

Author: [REDACTED]

Version Number:

7

Version Date:

07Dec2023

Template No.: CS_TP_BS016 Revision 6

Reference: CS_WI_BS005

Effective Date: 02Dec2019

Variable	Unit	Low	High
Heart rate	bpm	≤ 50 bpm AND decrease from baseline ≤ 15 bpm	≥ 120 bpm AND increase from baseline ≥ 15 bpm
Body temperature	°C	NA	≥ 38.3 °C AND increase from baseline ≥ 0.8 °C

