7 SAFETY AND ADVERSE EVENTS

7.1 Definitions

7.1.1 Adverse Events

An adverse event (AE) is defined as any untoward medical occurrence in a participant administered study drug, whether or not considered drug related. An adverse event can be any unfavorable and unintended sign (including abnormal laboratory findings), symptom, or disease temporally associated with the use of the study drug, whether or not considered related to

study drug. An adverse event can arise from any use of the drug and from any route of administration, formulation, or dose including an overdose.

Any medical condition that is present at the time the participant is consented but does not deteriorate should not be reported as an AE. However, if it deteriorates or worsens significantly at any time during the study, it should be recorded as an AE.

Clinically meaningful (for a given participant) changes in physical examination findings and abnormal objective test findings, e.g., laboratory, vital signs, ECG, imaging (e.g., definite new ARIA changes) should also be recorded as AEs. The criteria for determining whether an abnormal objective test finding should be reported as an AE are as follows:

1. Test result is associated with accompanying symptoms or is of clinical concern
2. Test result requires additional diagnostic testing or medical/surgical intervention
3. Test result leads to a change in study dosing or discontinuation from the study, significant additional concomitant drug treatment, or other therapy
4. Test result leads to any of the outcomes included in the definition of a SAE

Merely repeating an abnormal test, in the absence of any of the above conditions, does not meet criteria 2 above for reporting as an AE. Any abnormal test result that is determined to be an error does not require reporting as an AE.

NOTE: The following are not considered AEs or SAEs:

- **Preplanned surgeries or procedures:** Preplanned procedures (surgeries or therapies) that were scheduled prior to signing of informed consent are not considered AEs. However, if a preplanned procedure is performed early (e.g., as an emergency) due to a worsening of the pre-existing condition, the worsening of the condition should be captured appropriately as an AE. Complications resulting from any planned surgery should be reported as AEs.

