6.6. COMMON CALCULATIONS

Scores for CDR Global and CDR-SB will be reported based on the value entered in the database and will not be recalculated.

For quantitative measurements, change from baseline will be calculated as post-baseline assessment - baseline assessment. If either the baseline or post-baseline value is missing, the observation will not be included in the change from baseline summary.

EYO equals a subject's age at the clinical assessment minus this subject's estimated age at onset (AO). The details of the estimated AO are provided in the double-blind period SAP, Section 12.1.2, noting that Appendix III of this SAP will be used for analysis rather than the Appendix II in the double-blind SAP. CRF visit date will be used for the calculation of EYO to ensure a constant value across all tests within a visit.

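### Table D's Low vital-sign criteria are inverted as written: they flag small falls and omit large ones

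*SAP*

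**What the plan says.** Table D in SAP section 18.6.1 pairs an absolute limit with a change from baseline for each vital sign. The three Low cells read:

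- systolic pressure: "≤ 90 mmHg AND decrease from baseline ≤ 20 mmHg"
- diastolic pressure: "≤ 50 mmHg AND decrease from ≤ 15 mmHg"
- heart rate: "≤ 50 bpm AND decrease from baseline ≤ 15 bpm"

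The High cells point the other way. The systolic one, for example, is "≥ 180 mmHg AND increase from baseline ≥ 20 mmHg". The diastolic, heart-rate and temperature High cells likewise require a rise of at least 15 mmHg, 15 bpm and 0.8 °C. Temperature has no Low criterion.

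The criteria are described as predefined, and they feed one planned output in SAP section 18.6: "Incidence of post-baseline markedly abnormal values (blood pressure, heart rate, respiratory rate and temperature"). The same section also plans observed values and changes by visit, and states: "A listing of all vital sign data will be presented for the OLE".

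SAP section 6.6 gives the sign convention for quantitative measurements: "change from baseline will be calculated as post-baseline assessment - baseline assessment". A fall is therefore a negative change. Table D does not refer to that convention and states its Low thresholds as positive decreases.

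**The concern.** A two-part criterion of this kind is meant to pick out readings that are both extreme and clearly shifted from the participant's own baseline. The High column does that. The Low column, read literally, does the opposite: among low readings it keeps those that moved little and discards those that moved a lot. The pattern is the same in all three Low rows and reversed in all four High rows, so a stray character from text extraction is an unlikely explanation. The diastolic cell also lacks the word for what the decrease is measured from.

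At stake is the Low half of the incidence table. Someone reading it to look for hypotension or bradycardia during the open-label extension would see people who started low and stayed low, and would not see people who fell a long way. SAP section 6 requires analyses to follow the SAP and departures from it to be documented in the study report. A programmer who coded the sensible rule would therefore be departing from the text, and one who followed the text would produce the wrong table.

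**Working it through.** There is no stated figure to reproduce, so the check applies the printed rule to pairs of readings.

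**Inputs (Table D).** Limit L and change threshold d: systolic 90 and 20 mmHg; diastolic 50 and 15 mmHg; heart rate 50 and 15 bpm. Define fall = baseline − post-baseline.

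- Printed rule: post ≤ L and fall ≤ d.
- Rule mirroring the High column: post ≤ L and fall ≥ d.

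**Worked pairs.**

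| Measure | Baseline → post | Fall | Printed rule | Mirrored rule |
|---|---|---|---|---|
| Systolic | 130 → 85 | 45 | not flagged | flagged |
| Systolic | 106 → 85 | 21 | not flagged | flagged |
| Systolic | 105 → 85 | 20 | flagged | flagged |
| Systolic | 92 → 90 | 2 | flagged | not flagged |
| Diastolic | 80 → 45 | 35 | not flagged | flagged |
| Diastolic | 50 → 45 | 5 | flagged | not flagged |
| Heart rate | 85 → 45 | 40 | not flagged | flagged |
| Heart rate | 50 → 45 | 5 | flagged | not flagged |

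Among readings at or below the limit, the two rules agree only when the fall equals d exactly.

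**Baseline ceiling.** If post ≤ L and baseline − post ≤ d, then baseline ≤ L + d:

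- systolic: 90 + 20 = 110 mmHg
- diastolic: 50 + 15 = 65 mmHg
- heart rate: 50 + 15 = 65 bpm

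A participant above the ceiling cannot be flagged Low on that measure, however far the reading falls. This needs no assumption.

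**Could the sign convention rescue the text?** Let change = post − baseline, as in section 6.6.

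- change ≤ −d is the mirrored rule, but no minus sign is printed.
- change ≤ +d keeps large falls, but it also admits any low reading that fell slightly, stayed level or rose by up to d. The change condition then filters almost nothing.

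No reading that keeps the printed ≤ and the positive number matches the High column.

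**Illustrative size, systolic only.** The documents give no vital-sign distribution. Assumption: baseline and post-baseline are bivariate normal with the same mean (115 to 130 mmHg) and SD (13 to 15), and correlation 0.4 to 0.6. Over that grid:

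| Quantity | Range |
|---|---|
| Readings ≤ 90 with fall ≥ 20 (dropped) | 22% to 69% |
| Readings ≤ 90 with a smaller fall (counted) | 29% to 65% |
| Readings ≤ 90 with no fall (depends on coding) | 2% to 15% |
| Dropped readings as a share of all systolic readings | 0.04% to 2.2% |
| Participants with baseline above 110 | 63% to 94% |

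The dropped share is lowest at mean 115, SD 13, correlation 0.6 (22.4%) and highest at mean 130, SD 13, correlation 0.4 (69.5%).

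**The case against.** The strongest reply is that this is a lost minus sign in one descriptive table and that little follows from it. Several parts of that stand. By-visit changes and the full listing would still show large falls. Protocol section 7.1.1 has clinically meaningful "abnormal objective test findings, e.g., laboratory, vital signs, ECG" and similar results recorded as adverse events. SAP section 18 plans no between-group safety comparison unless specified. The arm's particular safety focus is on imaging abnormalities and injection-site reactions, and the final report is to be abbreviated after early termination. No endpoint or efficacy estimate changes.

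It is also fair that the program has not been seen. The table shells supplied with the SAP are not among the documents and might carry a working rule, and a programmer may have coded the intended one. The percentages rest on assumed distributions; only the baseline ceilings come from the SAP itself.

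None of this removes the defect. The printed text is the predefined rule, and nothing in the available documents corrects it. The low readings that would still be counted are mostly the small falls that a change condition exists to exclude. Nor are vital signs incidental: Protocol section 8.2 includes them among the major safety endpoints to be analysed.

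A separate gap is that the incidence table is to cover respiratory rate, for which Table D has no row. That needs its own answer and does not affect this point.

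**Conclusion.** The concern holds. As printed, all three Low criteria select the wrong readings, with certain baseline ceilings of 110 mmHg systolic, 65 mmHg diastolic and 65 bpm. The intended rule was probably a signed change at or below the negative threshold, but the SAP does not say so. Whether the produced table is wrong depends on how the rule was coded. If it was coded literally, the Low counts for blood pressure and heart rate are not usable. The consequence is limited to that table, and the omitted readings are probably few in absolute number. It should be corrected because a predefined safety rule ought to identify what it is meant to identify.

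**What to change.** In Table D, replace ≤ with ≥ in the change condition of the three Low cells, so that each requires a fall from baseline of at least the SAP's existing threshold: 20 mmHg systolic, 15 mmHg diastolic and 15 bpm. Restore the word baseline in the diastolic cell. A note that these equal changes of −20, −15 and −15 or lower under section 6.6 would remove any doubt about sign. This alters a reporting definition only and introduces no new threshold.

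Then compare the program with the corrected text. If it followed the printed rule, rerun the incidence table; if it already used the mirrored rule, record that in the study report.

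The cost is three symbols, one word, a check of one program and at most one rerun of a descriptive table.
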